## 16.5 Sample Size Considerations

The sample size for the Phase I/II study (i.e. a maximum of 50 subjects) is a sample size of convenience. The number of subjects in the proposed study is based on logistics/funding

# Master Protocol

provided by the Department of Defense Telemedicine and Advanced Technology Research Center (TATRC); it is not based on any formal power calculations. Results from this study may provide valuable information for quantifying the effects of leucine in this group of transfusion-dependent DBA subjects and may be useful in estimating the effect size necessary for appropriately designing future larger-scale Phase III clinical trials. However, in order to have some idea as to the precision of estimates that can be obtained from this study, when the sample size is 50, a two-sided 95% confidence interval for a single proportion using the large sample normal approximation will be no wider than  $50\% \pm 13.9\%$  i.e. the 95% confidence interval will range from at most, 36.1% to 63.9%.

## **17.0 RESEARCH MONITOR REQUIREMENT**

**17.1** Per DOD Directive 3216.2, all GREATER THAN MINIMAL RISK STUDIES require a Research Monitor. This individual should be a qualified physician, other than the Principal Investigator, not associated with the protocol, able to provide medical care to research volunteers for conditions that may arise during the conduct of the study, and who will monitor the volunteers during the conduct of the study. The research monitor plays a role in reviewing monitoring plans and unanticipated problems.

**17.2** The research monitor is required to review all unanticipated problems involving risk to subjects or others associated with the protocol and provide an unbiased written report of the event. At a minimum, the research monitor will comment on the outcomes of the event or problem. The research monitor will also indicate whether he/she concurs with the details of the report provided by the site principal investigator.

17.3 The Research Monitor has been identified as:

[name],  
at The Steven and Alexandra Cohen Children's Medical Center of New York  
[name]  
New Hyde Park, NY 11040  
[contact]  
[contact]  
E-mail: [contact]

## **18.0 SAFETY MONITORING**

### **18.1 Reporting of Adverse Events and Unanticipated Problems**

Information about all serious adverse events, which may be noted through history, investigator questioning, by physical examination, or by subject volunteering, will be reported to the Coordinating Center by [contact]) on the Severe Adverse Event (SAE) Reporting Form (Appendix I) and the local IRB **within 24 hours** of learning of the occurrence of the event.

### **18.2 Clinical Research Monitoring Services**

The Office of Research Compliance (ORC), located at The Feinstein Institute of Medical Research (FIMR) and part of the Coordinating Center will provide clinical research monitoring services.

**18.2.1** These services include good clinical practice regulatory review, subject case review of critical study data and processes including:

## Master Protocol

- Case report form completion and source document verification
- Protocol and informed consent compliance
- Protocol drug accountability

**18.2.2** The ORC agrees to provide primarily remote monitoring services for all performance sites according to the risk-based monitoring plan including the following:

- Site initiation: Prior to study start-up for good clinical practice (GCP) and protocol overview

- Follow-up monitoring: Within 2 weeks after the first subject is enrolled and then after every fifth subject is enrolled (for a minimum of 11 monitoring visits) in addition to targeted reviews as required

- Final monitoring: Study close out

**18.2.3** Reporting: Regular monitoring reports will be generated by the ORC after each review and will be provided to the respective performance site and Study PI. Resolution of queries and outstanding issues or concerns will be the responsibility of the individual performance site and local PI. The lead PI will be responsible for reporting incidents of IRB non-compliance to the North Shore-LIJ Health System IRB and for securing compliance at all trial sites.

### **18.3 Reporting to the U.S. Army Medical Research and Materiel Command**

**18.3.1** The protocol will be conducted in accordance with the protocol submitted to and approved by the ORP HRPO and will not be initiated until written notification of approval of the research project is issued by the ORP HRPO.

**18.3.2** Accurate and complete study records will be maintained and made available to representatives of the U.S. Army Medical Research and Materiel Command as a part of their responsibility to protect human subjects in research. Research records will be stored in a confidential manner so as to protect the confidentiality of subject information.

**18.3.3** Any deviation to the protocol that may have an effect on the safety or rights of the subject or the integrity of the study must be reported to the USAMRMC ORP HRPO as soon as the deviation is identified.

**18.3.4** Major modifications to the research protocol and any modifications that could potentially increase risk to subjects must be submitted to the USAMRMC ORP HRPO for approval prior to implementation. All other amendments will be submitted with the continuing review report to the USAMRMC ORP HRPO for acceptance.

**18.3.5** A copy of the approved continuing review report and the IRB approval notification will be submitted to the USAMRMC ORP HRPO as soon as these documents become available. A copy of the approved final study report and IRB approval notification will be submitted to the USAMRMC ORP HRPO as soon as these documents become available.

**18.3.6** The knowledge of any pending compliance inspection/visit by the FDA, DHHS-OHRP, or other government agency concerning clinical investigation or research, the issuance of Inspection Reports, FDA Form 483, warning letters or actions taken by any Regulatory Agencies including legal or medical actions and any instances of serious or continuing noncompliance with the regulations or requirements will be reported immediately to USAMRMC ORP HRPO.

### **18.4 SAE Definitions** An SAE is any untoward medical occurrence that:

**18.4.1** Results in death

## Master Protocol

**18.4.2** Is life-threatening (defined as an event in which the subject is at risk of death at the time of SAE; this does not refer to an event which hypothetically might have caused death if more severe)

**18.4.3** Requires inpatient hospitalization or prolongation of existing hospitalization

**18.4.4** Results in more frequent need for erythrocyte transfusions (more than pre-study)

**18.4.5** Results in persistence or significant disability or incapacity

**18.4.6** Results in overdose (defined as the intentional or accidental ingestion of study drug at any dose which is considered medically relevant and excessive)

**18.4.7** Is medically significant (defined as the event may jeopardize the subject and may require medical or surgical intervention to prevent one of the outcomes listed above)

**18.4.8** Any SAE occurring after the subject has signed the informed consent form, and until 12 weeks after the subject has stopped study participation, must be reported.

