## 6.7 Pregnancy/Lactation

Excessive leucine administration interferes with embryo development in rats. Scientific evidence for the safe use of branched chain amino acids during pregnancy and lactation is not available as there are no human data.

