## **9.2 Exclusion Criteria**

**9.2.1** Known hypersensitivity to branched chain amino acids

**9.2.2 Diagnosis** of an inborn error of amino acid metabolism disorder

**9.2.3 Prior** hematopoietic stem cell transplantation

**9.2.4 Pregnancy**, or plans to become pregnant during duration of trial

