### **12.2.2 Laboratory Examinations**

**12.2.2.1** CBC with platelet count, differential, and red cell indices

**12.2.2.2** Reticulocyte count

**12.2.2.3** Percent Hemoglobin F at baseline and then every 3 months and at study completion

**12.2.2.4** Hepatic transaminases, serum bilirubin, creatinine, and blood urea nitrogen

**12.2.2.5** Serum ferritin at baseline and then every three months and at study completion

**12.2.2.6** If female and of child-bearing potential, pregnancy test at baseline and every 3 months

**12.2.2.7** Plasma leucine level as well as levels of isoleucine and valine and an amino acid profile at baseline. Plasma leucine levels are obtained for research only and will not be used for clinical decision making. This extra blood will be drawn at the same time as standard routine clinical blood draws. A standard 10cc's (2 teaspoons) will be taken as part of clinical care, with an additional 5 cc's (1 teaspoon) taken after Leucine treatment begins to monitor leucine levels in the blood. Plasma leucine levels (5 cc's) will also be drawn at 2 weeks, 4 weeks, then months 3, 6, and 9 months (These are the extra tests for this study protocol. All the others are standard of care for the enrolled subjects.) Subjects will fast for 4 hours and hold the morning dose of Leucine for evaluation of the Leucine level at these time points. Blood drawings can be  $\pm$  7 days of the requested time, except week 2.

Laboratory examinations 12.2.2.1, 12.2.2.2, 12.2.2.4 and 12.2.2.5 are standard of care for transfused DBA subjects who are on chelation medication – which the chronically transfused subjects eligible for this protocol will be receiving; 12.2.2.3, 12.2.2.6 and 12.2.2.7 are extra tests that are specific to the study protocol. The instructions for sample collection and shipping of blood for amino acid levels are delineated in Appendix H. The blood samples will be batched and shipped directly from the participating institution to Case Western Reserve University, Ohio where the tests will be performed. The costs for the mailing will be provided by the Coordinating Center through a FedEx account.

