### 13.5.3 Dose Discontinuation

In the event of any serious adverse event (SAE), the study drug will be discontinued until all symptoms resolve. If the SAE is deemed possibly related to the protocol therapy, the subject will be removed from the study and leucine will be permanently discontinued.

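### The SAE criteria contain no birth-defect item, and no rule requires an on-study pregnancy to be reported promptly or followed to outcome, although the protocol excludes and tests for pregnancy

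*Combined protocol and SAP*

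**What the plan says.** **SAE criteria.** Section 18.4 gives seven criteria. The first is "Results in death". The second is a life-threatening event, "defined as an event in which the subject is at risk of death at the time of SAE". The others are inpatient or prolonged hospitalization, more frequent transfusion, disability, overdose, and a catch-all in 18.4.7: "Is medically significant (defined as the event may jeopardize the subject", with possible intervention to prevent one of the other outcomes. Under 18.4.8, SAEs from consent and "until 12 weeks after the subject has stopped study participation, must be reported". Section 18.1 sends SAEs to the Coordinating Center and local IRB within 24 hours.

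**Pregnancy.** Section 6.7 states: "Excessive leucine administration interferes with embryo development in rats". It adds that there are no human data. Section 9.1.5 requires a negative test in menstruating females, and contraception until at least 3 months after the last dose. Section 9.2.4 excludes pregnancy, "or plans to become pregnant during duration of trial". Section 12.2.2.6 requires, for females of child-bearing potential, a "pregnancy test at baseline and every 3 months".

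**Stopping.** Section 13.5.3 is triggered by an SAE: "In the event of any serious adverse event (SAE), the study drug will be discontinued until all symptoms resolve". Sections 15.1 to 15.4 cover subject choice, PI decision, drug-related toxicity and non-adherence. Pregnancy is not mentioned in 13.5.3, in 15.0 or anywhere in 18.0.

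**The concern.** The protocol treats pregnancy as a hazard at entry and looks for it during treatment, but says nothing about what follows when it is found. A birth defect in a subject's child meets no listed SAE criterion by name. The catch-all does not clearly reach it, because the child is not the subject. An uncomplicated pregnancy is not an SAE, so the 24-hour report is not triggered.

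Safety is a primary objective (4.1.3), and 16.4 plans to tabulate adverse events with confidence intervals. If pregnancies and births have no defined route into the safety data, a report of no reproductive harm could reflect the definitions rather than what happened. The protocol says human data are lacking, so any outcome that did occur would be worth having.

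**Working it through.** The plan gives no figure on this point, so there is none to reproduce. The main finding is a comparison of text; the timing of the window is secondary arithmetic.

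**1. Would a birth defect or pregnancy meet a stated rule?**

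- *18.4.1 to 18.4.6:* no birth-defect item. Death, hospitalization and disability name no person, but nothing extends them to offspring.
- *18.4.7:* tied to danger to the subject.
- *18.7.1:* ties an adverse event (AE) to someone receiving study drug.
- *18.1:* its heading also names unanticipated problems, but its text gives a procedure only for SAEs.
- *13.5.3 and 15.1 to 15.4:* none names a positive test.

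No criterion or reporting rule names either event.

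**2. What does reach the Coordinating Center?** The pregnancy test is listed under the Case Report Form (CRF) data in 12.2. Section 12.4 has these forms submitted every 3 months. A positive scheduled test can therefore arrive, but on a routine cycle and with no birth outcome attached. As printed, the schedule in 13.3 marks tests at baseline, month 3 and month 6 only.

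**3. When does the SAE window close relative to birth?**

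Inputs from the protocol:
- dosing lasts 9 months, about 39 weeks (13.0);
- the window runs 12 weeks past the end of participation (18.4.8);
- study length is 12 to 15 months, about 52 to 65 weeks, without saying whether this is each subject's participation (8.0);
- contraception runs at least 3 months, about 13 weeks, after the last dose (9.1.5).

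Assumption, not in the documents: 38 weeks from conception to birth, with 34 weeks as the lower end of the range.

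Formulas:
- window closes = end of participation + 12;
- latest conception delivering inside the window = closing week − 38;
- share of dosing affected = (39 − that week) / 39, not below 0.

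| Participation ends | Window closes | Latest conception inside | Share of dosing affected |
|---|---|---|---|
| 9 months (week 39) | 39 + 12 = 51 | 51 − 38 = 13 | 26/39 = 67% |
| 12 months (week 52) | 52 + 12 = 64 | 64 − 38 = 26 | 13/39 = 33% |
| 15 months (week 65) | 65 + 12 = 77 | 77 − 38 = 39 | 0/39 = 0% |

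At 34 weeks the latest conceptions become weeks 17, 30 and 43, and the shares become 22/39 = 56%, 9/39 = 23% and 0%.

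*Early departure.* If a subject leaves at a positive month 3 test (week 13), the window closes at 13 + 12 = week 25. The earliest term birth from a conception at first dose is week 38, so no such birth falls inside the window.

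*Contraception period.* If participation ends with the last dose, the 12-week window is about 1 week shorter than the 13-week contraception period.

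**4. How many subjects?** Enrollment is capped at 50. The registry ratio of 1.03:1.00 in 19.1.1 implies 1/2.03 = 49% female, or about 25. The number of child-bearing potential is not given, and 19.2 expects most subjects to be children.

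**The case against.** The strongest reply is that the protocol has other routes. The Research Monitor reviews unanticipated problems that put subjects or other people at risk (17.2). Deviations affecting safety go to the funder's human research office (18.3.3). Section 18.7.3 defines an AE broadly enough that an unintended pregnancy could be read into it, and 18.7.4 would then ask for its outcome if known. Section 18.5.5 asks for the outcome of AEs that led to permanent discontinuation or were present at study end. Non-adherence (15.4) might apply if the contraception agreement was breached. A complication that puts the mother in hospital is already an SAE. These routes are real, but all except the last depend on a site's reading, and none names pregnancy or birth.

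The reply does rule out several stronger readings that a reader might infer:

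- *That no pregnancy would ever reach the Coordinating Center.* Scheduled test results travel on the 3-monthly CRFs.
- *That the SAE list covers harm to the subject only.* Only 18.4.2, 18.4.6 (through ingestion of study drug) and 18.4.7 are clearly tied to the subject.
- *That leucine is a known embryo toxin at the trial dose.* Section 6.7 concerns rats and excessive intake, and section 7.0 places the trial dose well under the highest intake reported as safe in humans.
- *That two thirds of exposed births would be missed.* The 67% holds only if participation ends with dosing, which the protocol does not state.

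Appendix G (CRF), Appendix I (SAE form) and the consent pages were not available, and pregnancy wording there cannot be excluded. The number of subjects affected is probably small.

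**Conclusion.** The point holds on the text of the protocol body. There is no birth-defect criterion in 18.4, no duty to report a pregnancy promptly, and no follow-up to outcome, although four sections treat pregnancy as a hazard. This does not depend on the timing arithmetic: even if the window stayed open past every birth, a birth defect would still match no listed criterion by name.

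The 12-week limit adds to the gap by an amount the documents do not fix. The affected share of the dosing period is 0% to 67% for a completer, depending on when participation ends and assuming 38 weeks from conception to birth. For a subject who leaves at a positive month 3 test, the window closes before any term birth from an on-study conception.

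The matter bears on the completeness of the safety data. It does not affect the response estimates or the sample size. It should be corrected, with modest weight given the few subjects likely to be concerned.

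**What to change.** 1. Add to 18.4: *congenital anomaly or birth defect in the offspring of a subject*.
2. Add one sentence to section 18: any pregnancy conceived between the first dose and the end of the contraception period in 9.1.5 is reported to the Coordinating Center and the Research Monitor on the 18.1 timeline, and its outcome is recorded regardless of the limit in 18.4.8.
3. Reconcile 9.2.4, 12.2.2.6, 13.5.3 and 15.0 on what a positive on-study test leads to. The clinical rule is for the investigators to set.
4. Check Appendices G and I and the consent form for consistent wording.

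The cost is a protocol amendment with review at up to 17 institutions, a short form, and permission to collect outcome data on offspring for the few subjects affected. No new visit, test or change in sample size is needed.

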### 18.5 Assessment Terms for SAE and Causal Relationship to Study Drug

**18.5.1 DEFINITE** means there is a reasonable causal relationship between study drug and the SAE. The event responds to withdrawal of drug and recurs with re-administration of the study drug (if clinically feasible).

**18.5.2 PROBABLE** means there is a reasonable causal relationship between study drug and the SAE. The SAE tapers or diminishes once study drug has been discontinued. Re-administration of the study drug not required. Relationship between study drug and SAE cannot be reasonably explained by the known characteristics of subject's clinical state.

**18.5.3 POSSIBLE** means there is a reasonable causal relationship between study drug and the SAE but the SAE could have been produced by subject's clinical state or by other means of treatment or medications concurrently administered to the subject.

**18.5.4 UNLIKELY** means there is a temporal relationship to study drug administration but no reasonable causal relationship exists between study drug and SAE. The SAE does not follow a reasonable sequence from administration of study drug. SAE could have been produced by subject's clinical state or by other means of treatment or medications concurrently administered to the subject.

**18.5.5 UNRELATED** means there is no temporal relationship between SAE and study drug administration (e.g., the SAE occurred too early, too late, or study drug not taken) or there is reasonable causal relationship between SAE and another drug, concurrent disease, or circumstance and the SAE. Subjects experiencing AEs that cause an interruption or discontinuation of study drug or those who experience AEs that are present at the end of study should receive appropriate follow-up care. Sites should report the outcome of any AE that caused permanent discontinuation of the study drug or that was present at the end of the study.

### 18.6 Grades of Severity

**18.6.1 MILD** An event that is easily tolerated by the subject, causing minimal discomfort and not interfering with everyday activities.

**18.6.2 MODERATE** An event that is sufficiently discomforting to interfere with normal everyday activities.

**18.6.3 SEVERE** An event that prevents normal everyday activities.

### 18.7 Non-Serious Adverse Event (AE) Reporting

# Master Protocol

**18.7.1** An Adverse Event (AE) is *any* unexpected, non-serious event that is NOT an SAE. An AE is any untoward medical occurrence or worsening of a pre-existing medical condition in a subject who receives a study drug and which does not have a necessarily causal relationship with study treatment.

**18.7.2** A “study drug” is defined as a pharmaceutical form of an active ingredient being tested in this study.

**18.7.3** An AE, therefore, can be any unfavorable and unintentional sign (*including* a clinically significant abnormal laboratory finding, for example), symptom or disease associated with the use of the medicinal product, whether or not considered related to the medicinal product. The collection of Non-Serious AE information should begin at Day 1, initiation of study drug.

**18.7.4** All identified AEs must be recorded on the data capture forms, including description of AE, date and time of onset and resolution; duration of AE if less than 24 hours, severity of event, investigator’s opinion of the relationship of the study drug, study treatment action (if any), and outcome of AE (if known).

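### Section 18.7.1 gives two conflicting definitions of an adverse event, and aim 4 in 16.4 puts a confidence interval on a proportion of events rather than of subjects

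*Combined protocol and SAP*

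**What the plan says.** **Definition.** The first sentence of 18.7.1 confines an AE to any "unexpected, non-serious event that is NOT an SAE". The second calls it "any untoward medical occurrence or worsening of a pre-existing medical condition" in a subject who receives study drug. Section 18.7.3 repeats the broad sense, whether or not the event is thought related, and 18.7.4 adds: "All identified AEs must be recorded on the data capture forms".

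**Serious events.** SAEs are defined in 18.4 and reported within 24 hours under 18.1. They include any event that "Requires inpatient hospitalization or prolongation of existing hospitalization" (18.4.3) and, under 18.4.4, any event leading to more frequent red cell transfusion than before the study.

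**Windows.** For non-serious events: "The collection of Non-Serious AE information should begin at Day 1, initiation of study drug" (18.7.3). For SAEs, 18.4.8 runs from consent "until 12 weeks after the subject has stopped study participation, must be reported".

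**Analysis.** Safety is listed under the primary objectives (4.1.3). Aim 4 is stated in 16.2.4 as the frequency, severity and relatedness of AEs. Section 16.4 says only that the proportion of AEs will be tabulated with its 95% interval. Aim 1, in the same section, is written as a proportion of subjects. Section 16 does not mention SAEs.

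**Severity.** Sections 13.4 and 16.3 name CTCAE v4.0. Section 18.6 defines mild, moderate and severe without a map to CTCAE grades, and 18.7.4 asks for "duration of AE if less than 24 hours, severity of event" and further items without naming a scale.

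**The concern.** Two things are left open that decide what the safety table means.

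The first is which events enter it. Under the first sentence of 18.7.1, an expected event is not an AE and neither is an SAE. The events most likely to be called expected are the gastrointestinal symptoms that 6.5 attributes to oral leucine, which a safety table for this product should show. Section 18.7.4 does not settle the matter, because an instruction to record all identified AEs depends on what counts as one.

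The second is what is counted. A proportion of events has events in its denominator. It describes the mix of events, not the chance that a subject has one. A binomial interval on it also treats repeat events in one subject as independent, although the same subjects are seen at up to ten post-baseline visits.

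Two analysts following the text could therefore report different event sets and different quantities. Section 16.5 hopes that the results will help to design a Phase III trial, and for that the risk per subject is the usable figure.

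**Working it through.** **The plan's own figure.** Section 16.5 gives a worst-case 95% interval of 50% ± 13.9% at n = 50. Check: 1.96 × √(0.5 × 0.5 / 50) = 0.1386, so 36.1% to 63.9%. It reproduces. It is a general precision statement with 50 subjects as the denominator, and is not assigned to AEs.

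**Effect of the unit.** The documents give no AE counts, so these are assumed: 5 of 50 subjects have k nausea events each, and 20 other events occur in the trial. Post-baseline visits are weeks 2 and 4 and months 2 to 9 (12.2), which is 2 + 8 = 10 per subject and 50 × 10 = 500 in all. The per-visit column assumes at most one nausea event per visit.

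| k | Subjects: 5/50 | Share of events: 5k/(5k + 20), naive exact 95% | Per subject-visit: 5k/500 |
|---|---|---|---|
| 1 | 10% | 5/25 = 20.0% (6.8–40.7) | 1.0% |
| 2 | 10% | 10/30 = 33.3% (17.3–52.8) | 2.0% |
| 4 | 10% | 20/40 = 50.0% (33.8–66.2) | 4.0% |
| 8 | 10% | 40/60 = 66.7% (53.3–78.3) | 8.0% |

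The subject-level figure does not move with recurrence; the other two do. The columns are different quantities, so the gap between them is not an error in any one of them. It shows that the unit must be named.

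**Effect of clustering on an event-level interval.** Simulation with 5,000 runs, 50 subjects, gamma-Poisson counts with a mean of 3 AEs per subject, and a true share of 20% for one event type (all assumed). A nominal 95% normal-approximation interval over events covers the truth in 94% of runs with no within-subject correlation, 87% at a correlation of 0.1, 75% at 0.3 and 66% at 0.5.

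**Effect of the event set.** Assume that 20 of 50 subjects have any event and that 5 of them have only SAEs. With SAEs: 20/50 = 40% (exact 26.4–54.8). Without: 15/50 = 30% (17.9–44.6).

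**Intervals under the subject-level fix, n = 50.**
- 0/50, exact upper limit: 1 − 0.025^(1/50) = 7.1%. Wilson upper limit: z²/(n + z²) = 3.84/53.84 = 7.1%.
- 5/50, exact (Clopper-Pearson): 3.3–21.8%.
- 5/50, Wilson: centre (0.1 + z²/100)/(1 + z²/50) = 0.1285; half-width 1.96 × √(0.1 × 0.9/50 + z²/10,000)/(1 + z²/50) = 0.0851; limits 4.348% and 21.36%, so 4.3–21.4%.

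**The case against.** The best defence is that the broad definition governs. It fills the second sentence of 18.7.1, 18.7.3 draws its conclusion from it, and neither 18.7.4 nor the case report form item in 12.2.3 carries an expectedness limit. Section 18.7 is headed as non-serious event reporting, so its first sentence may only separate that route from the 24-hour SAE route. Elsewhere the plan uses the general term to cover SAEs: 18.1 and 13.5 are both titled for adverse events and contain SAE rules. On the unit, the trial has 50 subjects and 16.5 frames precision at n = 50, so a subject-level reading is natural. The analysis is descriptive, and no decision rule uses the AE proportion.

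Much of this stands. A reader might infer that foreseeable events and SAEs are lost to the trial. The documents do not support that: the text points both ways on foreseeable events, and SAEs are collected under 18.1 and 18.4.8. Nor do they support saying that the plan chose an event-level analysis with independent events; that follows only from the literal wording. The longer SAE window is a design choice, not an error.

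The defence does not remove the contradiction inside 18.7.1 or supply a unit for aim 4. Collecting SAEs does not say whether they enter the aim 4 proportion, and a descriptive result still needs a numerator and a denominator.

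**Conclusion.** The point holds as a defect of wording with consequences for the safety table. Section 18.7.1 states a rule that would under-record foreseeable events if followed, and contradicts it in the next sentence. Aim 4, read as written, counts events, and section 16 is silent on SAEs. The size of any under-count cannot be derived from the documents. Every figure above except the 13.9% check and the bare interval limits rests on assumed counts, and serves only to show that unit and event set matter.

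A reader might go further and infer that AEs will get a normal-approximation interval, which has zero width at 0/50. The plan does not say so: 16.5 uses that approximation for the precision statement only, and aim 4 names no method.

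The severity scale is a secondary point. The endpoint scale is already named as CTCAE v4.0, and 18.6 needs only to be reconciled with it. Appendices G (case report form) and I (SAE form) were not available and may name a scale or clarify event capture. A form would not ordinarily set the unit of analysis.

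**What to change.** 1. In 18.7.1, delete *unexpected*, and keep *non-serious* only as a label for the reporting route.
2. In 16.4, restate aim 4 as the number and percentage of dosed subjects with at least one AE, SAEs included, by type, worst CTCAE v4.0 grade and relatedness, with exact or Wilson 95% intervals. Give event counts beside them without a binomial interval.
3. Show SAEs in their own row. Show events that are SAEs only through 18.4.4 separately, because more frequent transfusion is also the efficacy category Progression in 16.3. Otherwise the overall AE percentage would mix lack of efficacy with harm.
4. State in the table the collection window for each class of event. The windows themselves need not change.
5. As a secondary step, reconcile 18.6 and 18.7.4 with 13.4 and 16.3. The discontinuation rules in 13.5.3 and 15.3 are not touched.

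The cost is wording in 18.6, 18.7.1, 18.7.4 and 16.4, with no new visits or tests. Whether the forms in Appendices G and I need a change cannot be judged without them. Reported AE percentages may be higher, and exact intervals are slightly conservative.
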